#### 3.2 STATISTICAL DECISION RULES

- *If a statistical test is required, it should be carried out at the two-side significant level 5%.*
- *When multivariable analysis is performed, independent variables used for actual analysis can be added or subtracted considering the structure of collected data and general characteristics of study subjects.*
- *When the analysis with propensity score matching is performed, paired t-test, McNemar's test, Linear mixed model, conditional logistic regression, etc. are used for analysis.*

PFIZER CONFIDENTIAL

## 4 ANALYSIS SETS/POPULATIONS

### 4.1 FULL ANALYSIS SET

All subjects that have satisfied the inclusion criteria and were registered for the study. Inclusion and exclusion criteria are outlined in the study protocol section 7.2.

### 4.2 SAFETY ANALYSIS SET

*Not Applicable*

[figure not shown]
### 4.3 OTHER ANALYSIS SET

*Not Applicable*

### 4.4 SUBGROUPS

*Not Applicable*

PFIZER CONFIDENTIAL

## 5 ENDPOINTS AND COVARIATES

Endpoints and covariates evaluated in this study are as follows:

[figure not shown]
### 5.1 EFFICACY/EFFECTIVENESS ENDPOINT(S)

Variable	Role	Data source	Operational definition
Treatment satisfaction	Outcome	Patient questionnaire	
 
▪ 14 questions applicable for treatment satisfaction measurement 
 
- Self-reporting questionnaire for evaluating treatment satisfaction
 
- Four domains including effectiveness, convenience, global satisfaction, and side effects
 
- Scores for each domain are calculated based on the equation
 
- Range of 0–100
 
 
 
▪ Higher numbers indicate higher treatment satisfaction
 

EQ-5D index	Outcome	Patient questionnaire	
 
▪ Standardized tool for measuring overall health
 
▪ EQ-5D index: 15 questions for assessing quality of life 
 
- Five domains, including mobility, self-care, usual activities, pain/discomfort, and anxiety/depression
 
- Scores for each domain are calculated based on the equation
 
 
 
▪ Higher scores indicate better health
 

EQ VAS	Outcome	Patient questionnaire	
 
▪ Standardized tool for measuring overall health
 
▪ EQ VAS: Value for evaluating overall health 
 
- Range of 0–100
 
 
 
▪ Higher scores indicate better health
 

### 5.2 SAFETY ENDPOINTS

*Not Applicable*

PFIZER CONFIDENTIAL

### 5.3 OTHER ENDPOINTS

*Not Applicable*

### 5.4 COVARIATES

Item	Variables	Role	Data source	Operational definition
Basic characteristics	Age	Covariate	Medical chart	▪ Used entered value
	Gender	Covariate	Medical chart	▪ Used entered value
Demographics	Educational level	Covariate	Patient questionnaire	▪ Used entered value
	Financial status	Covariate	Patient questionnaire	▪ Used entered value
	Employment status	Covariate	Patient questionnaire	▪ Used entered value
Clinical characteristics	Body mass index	Covariate	Medical chart	▪ Calculated as weight (kg) / height (m  )
	Comorbidities	Covariate	Medical chart	▪ Used entered value
	Duration of rheumatoid arthritis	Covariate	Medical chart	Days between initial diagnosis and assessed date calculated
	Erythrocyte sedimentation rate	Covariate	Medical chart	▪ Used entered value
	C-reactive protein level	Covariate	Medical chart	▪ Used entered value
	Tender joint count	Covariate	Medical chart	▪ Used entered value
	Swollen joint count	Covariate	Medical chart	▪ Used entered value
	Pain VAS score	Covariate	Medical chart	▪ Used entered value
	Previously used drugs	Covariate	Medical chart	▪ Used entered value
	Currently used drugs	Covariate	Medical chart	▪ Used entered value

PFIZER CONFIDENTIAL

Item	Variables	Role	Data source	Operational definition
	Treatment numbers	Covariate	Medical chart	▪ Used entered value
	Treatment dose	Covariate	Medical chart	▪ Used entered value
	Treatment duration	Covariate	Medical chart	▪ Days between treatment initiation and assessed date
	Concomitant csDMARDs use	Covariate	Medical chart	▪ Used entered value
	Number of concomitant csDMARDs	Covariate	Medical chart	▪ Assessed the number of drugs recorded
	Type of concomitant csDMARDs	Covariate	Medical chart	▪ Used entered value
	Dose of concomitant csDMARDs	Covariate	Medical chart	▪ Used entered value
	Duration of concomitant csDMARDs use	Covariate	Medical chart	▪ Used entered value ▪ Days between initial treatment administration and assessed date
	Concomitant NSAIDs use	Covariate	Medical chart	▪ Used entered value
	Number of concomitant NSAIDs	Covariate	Medical chart	▪ Assessed the number of drugs recorded
	Type of concomitant NSAIDs	Covariate	Medical chart	▪ Used entered value
	Dose of concomitant NSAIDs	Covariate	Medical chart	▪ Used entered value
	Duration of concomitant NSAIDs use	Covariate	Medical chart	▪ Used entered value ▪ Days between initial treatment administration and assessed date
	Concomitant steroid use	Covariate	Medical chart	▪ Used entered value
	Number of concomitant steroids	Covariate	Medical chart	▪ Assessed the number of drugs recorded
	Type of concomitant	Covariate	Medical	▪ Used entered value

PFIZER CONFIDENTIAL

Item	Variables	Role	Data source	Operational definition
	steroid		chart	
	Dose of concomitant steroid	Covariate	Medical chart	

▪ Used entered value

	Duration of concomitant steroid use	Covariate	Medical chart	

▪ Used entered value

▪ Days between initial treatment administration and assessed date

PFIZER CONFIDENTIAL

## 6 HANDLING OF MISSING VALUES

*In the case of data that do not have a bias in the interpretation of the results, the analysis is carried out based on only the observed data without adjusting the missing values. If it is deemed that significant bias is imposed on the interpretation of the results when the analysis is carried out with only the observed data, the analysis is carried out by statistically adjusting the missing values using the following appropriate missing value imputation method. As a method of replacing missing values, methods such as mean imputation, median imputation, probability imputation, regression imputation, ratio imputation, or multiple imputation are used depending on the pattern of missing values.*

## 7 STATISTICAL METHODOLOGY AND STATISTICAL ANALYSES

### 7.1 STATISTICAL METHODS

#### 7.1.1 Analysis of Continuous Data

Continuous data will be presented as the average, standard deviation, median, and range (minimum and maximum). When normal distribution of data cannot be assumed, data will be presented as median, range, and interquartile range. When group comparison is needed, the Student's *t*-test or analysis of variance (ANOVA) will be used for continuous variables, as long as there is no deviance from the assumption of normality. If normality assumption is not satisfied, non-parametric methods, such as the Mann-Whitney's U test or Kruskal-Wallis test, will be used. In this case, histograms for each continuous variable will be used to evaluate normality assumption, and the parametric evaluation will be referenced for reviewing the result. However, if data involve analysis after propensity score matching, the paired *t*-test (or a non-parametric method such as the Wilcoxon signed-rank test) will be substituted to suit the characteristics of the matched data.

#### 7.1.2 Analysis of Categorical Data

Categorical data will be calculated as frequency or percentage. When group comparison is needed, the chi-square test will be used for categorical variables; however, the Fisher's exact test, which is a non-parametric method, will be used if more than 20% of the expected cell frequency is less than 5%. However, if data involve analysis after propensity score matching, McNemar's test or the generalized McNemar's test will be substituted to suit the characteristics of the matched data.

### 7.1.3 Descriptive Analysis

Treatment satisfaction will be presented as average, standard deviation, median (interquartile range) and range (minimum, maximum) for each domain, and quality of life will be presented as average, standard deviation, median (interquartile range), and range (minimum, maximum) for the EQ-5D index and EQ VAS. Differences in patient demographic and clinical characteristic variables will be compared using the Student's *t*-test or ANOVA. If collected variables do not satisfy the assumptions needed for parametric validation, non-parametric methods such as the Mann-Whitney's U-test or Kruskal-Wallis test will be used for analysis. When patient characteristics are continuous, the Pearson's correlation analysis or Spearman's correlation analysis will be used to analyze the correlation with dependent variables. However, if data involve analysis by propensity score matching, analytical methods that suit this characteristic will be substituted.

### 7.1.4 Statistical Software

All statistical analyses will be performed using Windows SAS® version 9.4 (Cary, NC, USA)

## 7.2 STATISTICAL ANALYSES

### 7.2.1 Epidemiological Characteristics

Subject demographics and clinical characteristics will be presented in a table. Continuous data will be presented as the average, standard deviation, median, and range (minimum and maximum), and categorical data will be presented as frequency and percentage.

[figure not shown]
[figure not shown]
#### A. Demographics

1. Age
2. Gender
3. Education level
4. Financial status
5. Current employment

#### B. Clinical characteristics

1. Body mass index
2. Co-morbidities
3. Initial RA diagnosis date
4. Previously used types of DMARDs
5. Currently used DMARD (tofacitinib citrate or adalimumab), treatment numbers/duration/dose

PFIZER CONFIDENTIAL

6. Concurrently used drug types, numbers, and doses  
(csDMARDs/NSAIDs/steroid)
7. DAS28 components

### 7.2.2 Safety Analyses

*Not Applicable*

### 7.2.3 Analyses of Endpoints

[figure not shown]
#### 7.2.3.1 Propensity Score Matching

There are concerns of selection bias in the selection of the subject population in observational studies, and there are limitations in inferring correlations owing to the absence of randomization. Selection bias means there is a higher chance of subjects being assigned to a treatment arm based on a particular covariate, and this covariate can be a disturbing variable in establishing the difference between the treatment groups [37]. In order to balance the covariates between the groups, the propensity score method can be used. For example, a study by Bangalore et al. (2015) involved patients with polyvascular disease, and in this study, 1:1 matching was performed through propensity scores using demographic and clinical characteristics as matching variables to compare the mortality rate and risk ratio between CAGB and PCI groups. Although there was no significant difference in mortality rate, the PCI group had a higher risk of myocardial infarction than the CAGB group [38].

In this study, the difference in treatment satisfaction and quality of life scores between the two groups that have been matched by propensity score will be compared. Propensity scores will be calculated using subjects' demographic and clinical characteristics as covariates. Matching will be done using the greedy matching (nearest neighbor) method. Assuming the ratio of 2:1, the greedy matching method will randomly select one subject from treatment group 2 and set a range of propensity scores using treatment group 2 as the center through the caliper. Two subjects from treatment group 1 that have the closest propensity scores will be selected. In this case, the caliper will be determined after reviewing the data. If more than 25% of the standard group is eliminated after matching or if the distribution of covariates in the two groups are thought to be different, inverse probability of treatment weighting (IPTW) can be used for analysis.

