7.3.1. Propensity score methods

The purpose of the propensity score is to create conditions similar to those of randomized trials by balancing the covariates in subjects between the groups. The propensity score adjustment method reduces multidimensional covariates into a one-dimensional score, or the propensity score. The computed propensity score can be used for bias reduction through restriction, matching, stratification, covariate adjustment, and weighted methods. It can also be used to estimate the mean treatment effect of two groups or the mean treatment effects of the active group compared to those of the control group.

- **Propensity score use of the propensity score in the cross-sectional studies [26-30]**

The propensity score is used in the cross-sectional studies to remove or minimize effects from the disturbance variable. Analytical methods using propensity scores are considered superior to the average covariate analysis method of the one-dimensional study. Therefore, the analytical method using propensity score will be used in this study.

1) *Propensity score matching* [25]

- Propensity score matching can restrict variations between the covariates by matching subjects with similar propensity scores from groups 1 and 2.
- Duplicates not allowed: Once a subject from group 2 is matched with a subject from group 1, he/she cannot be considered for a match to a subject from another group, and therefore, the subject from group 2 can be matched for a maximum of one time.
- Greedy matching (nearest matching method): Subject from group 1 is randomly selected; then the subject with the closest propensity score is selected from group 2 (caliper matching is also an option), and 1:1 matching will be considered.
- If too many subjects are eliminated from the analysis after matching, this method will not be considered as the analytical method, and only the methods described below will be considered and reported. Standards for the decision will be described in the SAP in detail.

2) *Propensity score adjustment* [28]

This method uses all patients enrolled in the study,

- **Propensity score adjustment:** A method for including the treatment variable and the PS itself as a covariate in a multiple model estimating a treatment effect.

3) **Propensity score based weighing** [28]

This method also uses all patient data.

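### At the equal group sizes planned, the SAP's 2:1 matching without reuse leaves at least half of group 2 unmatched and gives 1.5 times the variance of the protocol's 1:1 matching

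*SAP*

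**What the plan says.** **Protocol 7.3.1** describes greedy nearest-neighbour matching. A group 1 subject is drawn at random and paired with the closest group 2 subject, "and 1:1 matching will be considered", and a group 2 subject may be used only once. On losses it says: "If too many subjects are eliminated from the analysis after matching, this method will not be considered as the analytical method". In that case only the other propensity methods are to be reported. It adds: "Standards for the decision will be described in the SAP in detail".

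**SAP 7.2.3.1** reverses the index group and changes the ratio: "Assuming the ratio of 2:1, the greedy matching method will randomly select one subject from treatment group 2". The caliper is centred on that index subject's score, and the partners come from the other group: "Two subjects from treatment group 1 that have the closest propensity scores will be selected". It gives no reason for 2:1 and is silent on reuse. The caliper is to be chosen after the data are reviewed. The loss rule reads "If more than 25% of the standard group is eliminated after matching" (or if the covariate distributions are judged to differ), in which case "inverse probability of treatment weighting (IPTW) can be used for analysis".

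**Sample size (protocol 7.5, SAP 1.1.2).** Both sections use an equal-allocation formula. They arrive at 360 per group and plan to identify about 420 per group, 840 in total. Neither allows for matching loss or for a 2:1 ratio.

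**Tests for matched data.** SAP 7.1.1 names the paired t-test or Wilcoxon signed-rank test, and 7.1.2 names McNemar's test or an undefined generalized form. SAP 3.2 lists the paired t-test, McNemar's test, a linear mixed model and conditional logistic regression. SAP 7.2.3.2 specifies the linear mixed model for treatment satisfaction. SAP 7.2.3.3 leaves the matched method for quality of life open.

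**The concern.** A 2:1 match suits a study in which one group is much larger than the other. Here the planned groups are about equal, so each matched set uses up group 1 twice as fast as group 2, and half of group 2 has no partner left even with perfect overlap of propensity scores. The matched comparison then rests on fewer subjects than the protocol's 1:1 would use.

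The loss rule should catch this, but it is not clear which group it monitors, and exceeding the limit only permits IPTW. Whether the matched result or the weighted result carries the comparison could therefore be decided after the data are seen.

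**Working it through.** **Inputs.** Difference 4 points (83 − 79), pooled SD 14.58 to 19.1, two-sided 5% (z = 1.96), 80% power (z = 0.842), 360 per group: protocol 7.5 and SAP 1.1.2. Matching ratios: protocol 7.3.1 and SAP 7.2.3.1.

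**1. The plan's own figures.** N = 2·SD²/4² · (1.96 + 0.842)².
- SD 14.58: 2 × 212.58/16 × 7.851 = 208.6, so 209, as stated.
- SD 19.1: 2 × 364.81/16 × 7.851 = 358.02, so 359, as stated. The plan rounds this to 360, so SD 19.1 set the sample size.

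**2. Forced loss under 2:1 without reuse.** Group 1 of size n1 forms at most n1/2 sets, so the unmatched share of group 2 is at least 1 − (n1/2)/n2. With n1 = n2 = 360 this is 1 − 180/360 = 50%, before any caliper. It exceeds 25% whenever n1/n2 is below 1.5.

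**3. Variance.** Let n be the size of each group and ρ a common within-set correlation.
- 1:1, n pairs: 2·SD²(1 − ρ)/n.
- 2:1, n/2 sets: each set contributes SD²(1 + (1 + ρ)/2 − 2ρ) = 1.5·SD²(1 − ρ). Dividing by n/2 gives 3·SD²(1 − ρ)/n.

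The ratio is 3/2 = 1.5, whatever the SD or ρ.

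**4. Power** = Φ(4/(SD·√(1/a + 1/b)) − 1.96), with all of group 1 matched, no caliper loss and ρ = 0.

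| Available per group | SD | 2:1 | 1:1 |
|---|---|---|---|
| 360 | 19.1 | 360 v 180: 63.1% | 360 v 360: 80.2% |
| 360 | 14.58 | 85.2% | 95.7% |
| 420 | 19.1 | 420 v 210: 69.8% | 420 v 420: 85.9% |
| 420 | 14.58 | 90.1% | 97.8% |

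For the first row: 19.1·√(1/360 + 1/180) = 1.744, 4/1.744 = 2.294, Φ(0.334) = 0.631; and 19.1·√(2/360) = 1.424, 4/1.424 = 2.810, Φ(0.850) = 0.802. The difference detectable with 80% power is 2.802 × 1.744 = 4.9 points under 2:1 and 2.802 × 1.424 = 4.0 points under 1:1.

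**5. Sensitivity to ρ (assumed; the documents give none).** At SD 19.1 and 360 per group, ρ = 0.1 raises 2:1 to 67.7%. Power of 80% needs 1 − ρ = (4/2.802)² × 360/(3 × 364.81) = 0.67, that is ρ of about 0.33.

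**6. Unequal groups (assumed splits of 720, group 1/group 2, SD 19.1).**
- 288/432: 53.7% (2:1) v 71.0% (1:1), with 66.7% of group 2 unmatched under 2:1.
- 432/288: 71.0% v 71.0%, with 25% unmatched under 2:1.
- 480/240: 75.5% v 63.1%, with no forced loss.

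The two ratios break even at n1/n2 = 1.5. Only from 2 upward can every group 2 subject in principle receive two matches.

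**The case against.** The strongest defence is that nothing fixes the enrolled ratio. The study is non-interventional, 420 per group is a recruitment target, and SAP 1.1.2 reproduces the protocol's sample-size text, so it is not a second, independent plan. The SAP's ratio is worded as an assumption. The SAP is dated 12 March 2020, shortly before data collection was due to end on 31 March 2020, so 2:1 could be illustrative or could reflect enrolment visible by then. If group 1 were twice group 2, 2:1 would be the better choice. All this stands as possibility, but the SAP says none of it, and equal groups are the only sizes either document plans.

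The protocol's 1:1 wording is also soft, and protocol 7.7 lets the SAP modify the plan. A reader might infer that the SAP breaches the protocol; the documents do not support that. The problem is that the changed ratio does not fit the sizes the SAP itself carries over.

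A reader might take 63.1% as a ceiling or a floor. It is neither: positive within-set correlation raises it and caliper loss lowers it. It also uses the high end of the SD range; at SD 14.58, 2:1 keeps more than 80%.

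A reader might also say that the 25% limit is certain to be exceeded. That depends on what 'standard group' means. Group 2 is likely, since the caliper is centred on it, but the term is undefined. If group 1 is meant, the limit may never be reached although half of group 2 is dropped.

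Finally, it would be too strong to say that the SAP has no method for sets of three or for quality of life. The linear mixed model and conditional logistic regression in SAP 3.2 apply to matched analyses generally. What remains is that the pair-only tests are listed beside them without saying which applies at 2:1.

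**Conclusion.** The point holds for the matched analysis and should be fixed. With equal groups and no reuse, 2:1 discards at least half of group 2 and multiplies the variance of the matched difference by 1.5 relative to 1:1. At 360 per group, with no caliper loss and independent outcomes, that means 63.1% against 80.2% power at SD 19.1 and 85.2% against 95.7% at SD 14.58. The variance ratio does not depend on the SD or on a common within-set correlation; the power figures do.

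The conclusion rests on approximately equal enrolment, as planned, and on no reuse, which the protocol states and the SAP does not contradict. It does not follow that the study as a whole is underpowered: full-sample regression (SAP 7.2.4) and the weighting, covariate-adjustment and stratification methods (protocol 7.7.2) use all subjects and are unaffected.

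**What to change.** In SAP 7.2.3.1:

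- Use 1:1 matching without replacement, as in the protocol, unless the enrolled counts, looked at before any outcome, show one group at least twice the other. In that case 2:1 may be used with the smaller group as index.
- Define treatment groups 1 and 2 (protocol 7.2.2 lists tofacitinib citrate users first and adalimumab users second), the index group, and 'standard group' as the index group.
- State that IPTW will, not can, be used when more than 25% of that group is lost, in line with protocol 7.3.1.
- If 2:1 is used, apply the linear mixed model or conditional model already listed in SAP 3.2 to all outcomes, including the EQ-5D index and EQ VAS, in place of the pair-only tests in 3.2, 7.1.1 and 7.1.2.
- Report precision from the actual matched counts.

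This costs SAP wording only and no new data. There are three drawbacks. First, 1:1 gives up some power if the enrolled ratio (group 1/group 2) falls between 1.5 and 2. A cut-off of 1.5 would not be better at its lower end: there, 2:1 gains no power and already uses the whole 25% allowance before any caliper. Second, the index group determines which treatment population the matched estimate describes, and the SAP should say so. Third, 1:1 does not guarantee 80% power either: at 360 per group the tolerated 25% loss leaves 0.75 × 360 = 270 pairs, which gives 68.2% at SD 19.1 with independent outcomes.

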7.7.2. Outcomes comparison using propensity score methods

Differences in treatment satisfaction and quality of life between the two groups will be compared after adjusting for the demographic characteristics. Of the propensity score methods, we will be utilizing the matching, weighted, covariate-adjusted, and stratified methods. The propensity score will be estimated and used to balance the covariates between the groups. After the quality evaluation to assess whether the covariates are well balanced, treatment satisfaction and quality of life score with propensity score adjustment will be compared. Along with the various propensity score methods, multivariate linear regression will also be used to compare the results between the groups.

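### The SAP leaves the caliper, the balance criterion, the switch to IPTW and the primary estimator open, and nothing keeps TSQM and EQ-5D from those who decide them

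*SAP*

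**What the plan says.** SAP 7.2.3.1 describes greedy 2:1 matching within a caliper, centred on treatment group 2. On the width it says: "In this case, the caliper will be determined after reviewing the data". Two conditions allow a change of method. One is numeric: "If more than 25% of the standard group is eliminated after matching". The other is a judgement: "if the distribution of covariates in the two groups are thought to be different". If either holds, "inverse probability of treatment weighting (IPTW) can be used for analysis". The propensity model is described only as using demographic and clinical characteristics; SAP 5.4 lists more than 30 candidate covariates. The standardized mean difference is in the abbreviation list, but no threshold for it appears anywhere.

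Protocol 7.3.1 considers 1:1 matching and does not allow duplicates. For the case where matching eliminates too many patients, it says: "Standards for the decision will be described in the SAP in detail".

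Three places describe the comparison, and none calls an estimator primary:

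- Protocol 7.7.2: "we will be utilizing the matching, weighted, covariate-adjusted, and stratified methods", with linear regression alongside.
- SAP 7.2.3.1: a comparison of matched groups, with weighting as the optional fallback.
- SAP 7.2.4: linear regression on the full analysis set for all three outcomes.

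SAP 3.2 adds that in multivariable analysis "independent variables used for actual analysis can be added or subtracted considering the structure of collected data"; the sentence goes on to name patients' general characteristics as a second consideration.

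**The concern.** Propensity methods imitate a randomised design only if the design stage (model, caliper, balance check, choice of method) is finished without sight of the outcome. In this cross-sectional study TSQM and EQ-5D are collected together with the covariates, some of them through the patient questionnaire. Protocol 7.6.3 has one central database locked before analysis. Whoever reviews the data to set the caliper can have the outcomes in the same file, and neither document says otherwise.

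Two things are at stake. First, if several defensible analyses are available and none is fixed as primary, a nominal 5% test need not have a 5% error rate. Second, the methods need not answer the same question. Matching centred on group 2 estimates the effect in those group 2 patients who find matches. The weighting in Protocol 7.3.1 aims at a mean effect over the two drug groups. If the drug difference varies with patient characteristics, changing the method changes the target.

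**Working it through.** **1. The plan's own figures.** Inputs from Protocol 7.5 and SAP 1.1.2: difference 4, z-values 1.96 and 0.842, SD 14.58 or 19.1.

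N = 2σ²/(μ1−μ2)² × (1.96+0.842)²

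- SD 14.58: 2 × 212.58 / 16 × 7.851 = 208.6, rounded up to 209 (stated 209).
- SD 19.1: 2 × 364.81 / 16 × 7.851 = 358.02, rounded up to 359 (stated 359).
- Inflation: 360/0.90 = 400 and 360/0.80 = 450. The plan takes 420 per group, 840 in total.

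So the study is sized on a two-sided 5% test of one comparison.

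**2. What is fixed and what is open.**

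| Choice | State in the documents |
|---|---|
| Caliper | Expressly set after data review |
| Balance criterion | Judgement, no threshold |
| Loss trigger | More than 25%, denominator undefined, depends on the caliper |
| Switch to IPTW | Permitted, not required |
| Propensity covariates | Class named, no model |
| Matching ratio | 1:1 considered (protocol), 2:1 (SAP) |
| Primary estimator | None named |
| Order of work | Balance check before outcome comparison (Protocol 7.7.2) |
| Withholding of outcomes | No statement |

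**3. How the 25% trigger behaves.** Assume that the protocol's ban on duplicates carries over to the SAP's 2:1 scheme. With n1 and n2 patients in groups 1 and 2, at most min(n2, n1/2) of group 2 can be matched.

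- 420:420: at most 210 of 420, so at least 1 − 210/420 = 50% of group 2 is lost at any caliper.
- 504:336: at most 252 of 336, a loss of at least 25%.
- 560:280: at most 280 of 280, a loss of at least 0%.

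If group 2 is the standard group, the trigger can be avoided only when 1 − n1/(2·n2) ≤ 0.25, that is n1 ≥ 1.5·n2. At the planned 420 per group it always fires, and whether to switch then depends only on the permissive wording. If group 1 is the standard group, 2:1 matching at 420:420 could in principle use all 420 of it, and the trigger need not fire. The undefined term therefore decides the outcome of the one numeric rule.

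**4. Size of the error-rate problem (illustration).** The SAP carries three estimators: matching, IPTW and regression. Assume that under no true difference their test statistics are standard normal with common correlation r, and that the smallest p-value is reported.

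P(any |z| > 1.96) = 1 − ∫ [Φ((1.96−√r·u)/√(1−r)) − Φ((−1.96−√r·u)/√(1−r))]³ φ(u) du

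- r = 0.80: 9.8%
- r = 0.90: 8.4%
- r = 0.95: 7.3%

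The limits are 5% at r = 1 and 1 − 0.95³ = 14.3% at r = 0. The documents give no correlations; these are assumptions.

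**5. Cross-check by simulation.** This used 1,200 null datasets per scenario, SD 19.1, eight assumed covariates with five shifted by 0.15 SD, and enrolment of 420:420 and 560:280. One analysis fixed in advance (caliper 0.2 SD of the logit propensity score) rejected in 3.8% and 4.4% of runs. Choosing between that match and IPTW gave 5.7% in both. Choosing among four calipers, IPTW and regression gave 11.0% and 9.6%. The Monte Carlo standard error is about 0.9 points. The matching order was redrawn for each caliper, which inflates the last figures somewhat.

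**The case against.** Much can be said for the plan.

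- Protocol 7.7.2 puts the balance check before the comparison of outcomes, and both switch conditions can be evaluated without TSQM or EQ-5D. Tuning a caliper for balance without sight of outcomes is ordinary practice. This stands. What is missing is a criterion to tune to and a statement that outcomes are withheld.
- A reader might infer that every one of these choices is expressly made after looking at outcomes. The text does not support that. Only the caliper carries such wording, and it does not say that outcomes are among the data reviewed. The balance and IPTW clauses are imprecise rather than expressly post hoc. The covariate clause in SAP 3.2 points also to patients' general characteristics and governs multivariable models, not expressly the propensity model.
- A reader might also infer that the SAP ignored the protocol's promise of decision standards. It did not: the promise concerned losing too many patients in matching, and the SAP answers with 25%. The defects are the undefined denominator and the optional consequence.
- Counting all five methods in the protocol would give 8.5% to 12.7% at the same correlations. That overstates the case. The SAP carries three, and Protocol 7.7.2 says its methods will be used, which reads as reporting several analyses rather than picking one.
- SAP 3.1 states that there is no statistical hypothesis. This softens the error-rate argument but does not remove it: SAP 3.2 keeps a two-sided 5% level and the sample size rests on it. The change of target population matters with or without a test.

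**Conclusion.** The concern holds in this form. The caliper is set after data review, balance has no numeric criterion, the switch to IPTW is optional, the one numeric trigger refers to an undefined group, and no primary estimator is named. Nothing keeps the outcomes from those who decide. The plan permits a result-driven estimate and a shift of target population; it does not show that anyone intends either.

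The size, about 7% to 10% instead of 5%, is an illustration. It requires three candidate analyses, correlations of 0.8 to 0.95, and selection by p-value, all of which are assumptions. With only two closely related candidates the simulated inflation was small (5.7%). The loss of at least 50% of group 2 at 420:420 is arithmetic, given 2:1 matching without duplicates. The change of target population cannot be quantified from the documents. The point should be corrected before analysis, mainly because protection is cheap.

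**What to change.** Amend SAP 7.2.3.1 and 7.2.4, before outcomes are seen, as follows:

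1. Build the propensity model and the matched or weighted file on a dataset without TSQM and EQ-5D; merge the outcomes only after that file is frozen.
2. Fix the propensity covariate list.
3. Fix one caliper, for example 0.2 SD of the logit propensity score, and one balance criterion, for example an absolute standardized mean difference of at most 0.10. These values are proposals; any value fixed beforehand serves. With a long covariate list some will exceed the limit, so state what degree of failure triggers the switch and handle remaining imbalance by covariate adjustment.
4. Reconcile the 1:1 and 2:1 ratios and define the standard group. Do this before step 5: with 2:1 matching at 420:420 and group 2 as the standard group, a mandatory 25% rule would always discard matching.
5. Make the switch to IPTW mandatory when the rule fails, with weights that target the same population as the match and robust standard errors.
6. Name one primary estimator; report the others as sensitivity analyses.

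The cost is SAP wording and the order of programming, with no new data or patients. The downside is that a fixed caliper may lose more patients than a tuned one.
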